APPENDIX E. Ethical Standards**Ethics and Regulatory Considerations**

This study will be conducted according to Good Clinical Practice (GCP), US 21 Code of Federal Regulations (CFR) Part 50, (Protection of Human Subjects), US 21 CFR Part 56 (Institutional Review Boards), International council for Harmonisation Guidance for Industry, E6 Good Clinical Practice: Consolidated Guidance, the Nuremberg Code, and the Declaration of Helsinki.

General Instructions

The U.S. Food and Drug Administration (FDA) regulates studies of drugs, biologics, and medical devices. Consequently, these studies are subject to GCP and FDA regulations and guidance issued by the FDA and are included in, but not limited to, the following parts of the CFR and guideline document:

- 21 CFR Part 11 – Electronic Records; electronic signatures
- 21 CFR Part 50 – Protection of Human Subjects
- 21 CFR Part 54 – Financial Disclosure
- 21 CFR Part 56 – Institutional Review Boards
- 21 CFR Part 312 – Investigational New Drug Application
- FDA Guidance for Industry: Oversight of Clinical Investigations —A Risk-Based Approach to Monitoring, August 2013
- FDA Guidance for IRBs, Clinical Investigators, and Sponsors, June 2010
- FDA Guidance for Industry: Investigator Responsibilities – Protecting the Rights, Safety, and Welfare of Study Subjects, October 2009
- FDA Guidance for Industry and Investigators: Safety Reporting Requirements for INDs and BA/BE studies, December 2012
- Guidance for Industry E6 Good Clinical Practice: Consolidated Guidance, 2018

Copies of these materials are available from the sponsor upon request. The purpose of these regulations and legal obligations is to define the standards and principles for the proper conduct of clinical trials that have been developed by the medical, scientific, and regulatory communities. They are not intended to impede or restrict clinical research.

The ethical standards defined within GCP are intended to ensure that:

- Human subjects are provided with an adequate understanding of the possible risks of their participation in the study, and that they have a free choice to participate or not;
- The study is conducted with diligence and in conformance with the protocol in such a way as to insure the integrity of the findings;
- The potential benefits of the research justify the risks.

FPHU is the sponsor of the Investigational New Drug Application (IND). The sponsor, or designee, if regulatory obligations have been transferred, is responsible for the following:

- Selecting qualified investigators,
- Providing investigators with the information they need to properly conduct an investigation,

- Ensuring proper monitoring of the investigation,
- Ensuring that the study is conducted according to the general investigational plan and protocols contained in the IND,
- Maintaining the IND, and
- Ensuring that FDA and all participating investigators are properly informed of significant new information regarding adverse effects or risks associated with the drug being studied.

APPENDIX F. Investigator Obligations

Per Title 21 of the US Government Code of Federal Regulations (21 CFR) Parts 50 and 56, the study protocol and the final version of the patient informed consent form will be approved by the institutional review board (IRB) before enrollment of any patients. The opinion of the IRB will be dated and given in writing. A copy of the letter of approval from the IRB and a copy of the approved informed consent form will be received by the sponsor prior to shipment of study drug supplies to the investigator.

The investigator will ensure that the IRB will be promptly informed of all changes in the research activity and of all unanticipated problems including risk to patients. The investigator will also ensure that no changes will be made to the protocol without IRB approval.

As a part of the IRB requirement for continuing review of approved research, the investigator will be responsible for submitting periodic progress reports to the IRB at intervals appropriate to the degree of patient risk involved, but no less than once per year.

Written informed consent must be given freely and obtained from every patient prior to clinical trial participation. The rights, safety, and well-being of the trial patients are the most important considerations and should prevail over interests of science and society.

As described in GCP guidelines and FDA regulations, study personnel involved in conducting this trial will be qualified by education, training, and experience to perform their respective task(s). An FDA Form 1572 will be collected, listing the principal investigator and sub-investigators involved in the study. Study personnel will not include individuals against whom sanctions have been invoked after scientific misconduct or fraud (eg, loss of medical licensure, debarment). Quality assurance systems and procedures will be implemented to assure the quality of every aspect of the study.

Informed consent must be obtained from every patient before entry into a clinical study. It must be given freely and not under duress. Consent must be documented by use of an IRB-approved consent form and signed by the patient or the patient's legally authorized representative. The Department of Health and Human Services suggests that when minors are involved, a parent or guardian should sign the consent form. If the minor is an adolescent, his signature should also be included. Non-English-speaking patients must be presented with a consent form written in a language that they understand. A copy of the signed consent form must be given to the patient signing it. Another copy must be kept in the investigator's files and made available to and FDA representatives upon request. If, for any reason, patient risk is increased as the study progresses, a revised, IRB-approved consent form must be signed by the patient. Before the study begins, a sample of the consent form must be provided to the sponsor for review. The FDA may reject otherwise scientifically valid studies if proper informed consent has not been obtained from all patients.

Only in the case of a life-threatening incident may an investigational product be used without prior signed consent. In such an emergency situation, separate certifications must be written both by a physician not participating in the study and by the investigator. The certifications, along with the protocol and informed consent, must be sent to the IRB within 5 working days. In this situation, the investigator may not administer any subsequent product to that patient until informed consent and IRB approval are obtained.

Informed Consent

Written informed consent must be obtained from each patient prior to entry in the study. One copy of the signed informed consent document will be given to the patient, and another will be retained by the investigator. Additionally, the participant must be allowed adequate time to

consider the potential risks and benefits associated with his/her participation in the study. The signed and dated consent must be retained with the study records and a copy provided to each participant.

In situations where the participant is not legally competent to provide consent (ie, mentally incapacitated), written consent must be obtained from a parent, legal guardian, or legal representative. In these situations, the consent must be signed and dated by a witness.

The informed consent document must have been reviewed and approved by the sponsor and by the investigator's IRB prior to the initiation of the study. The document must contain the eight basic elements of informed consent and may contain the six additional elements described in 21 CFR Part 50. The attached Declaration of Helsinki-provides further details regarding the specific requirements for informed consent. Every consent form must include the following eight elements:

- A statement that the study involves research, an explanation of the purpose of the research and the expected duration of the patient's participation, a description of the procedures to be followed, and identification of any procedures that are experimental
- A description of any reasonably foreseeable risks or discomforts to the patient
- A description of any benefits to the patient or to others that may reasonably be expected from the research
- A disclosure of appropriate alternative procedures or course of treatment, if any, that might be advantageous to the patient
- A statement describing the extent, if any, to which confidentiality of records identifying the patient will be maintained and noting the possibility that the FDA and representatives may inspect the records
- An explanation as to whether any compensation or medical treatments are available if injury occurs for research involving more than minimal risk. The explanation should involve a description of the compensation or treatment available, or a statement describing where further information may be obtained
- An explanation of whom to contact for answers to pertinent questions about the research and the patient's rights and whom to contact in the event of a research-related injury
- A statement that participation is voluntary, that refusal to participate will involve no penalty or loss of benefits to which the patient is otherwise entitled, and that the patient may discontinue participation at any time without penalty or loss of benefits to which the patient is otherwise entitled.

Additional Elements of Informed Consent

When appropriate, one or more of the following elements of information shall also be included in the consent form:

- A statement that the particular treatment or procedure may involve risks to the patient (or to the embryo or fetus, if the patient is or may become pregnant) which are currently unforeseeable
- Anticipated circumstances under which the patient's participation may be terminated by the investigator without regard to the patient's consent
- Any additional costs the patient may incur from participation in the research

- The consequences of a patient's decision to withdraw from the research and procedures for orderly termination of participation by the patient
- A statement that significant new findings developed during the course of the research that may relate to the patient's willingness to continue participation will be provided to the patient
- The approximate number of patients involved in the study

Nothing in these regulations is intended to limit the authority of a physician to provide emergency medical care to the extent the physician is permitted to do so under applicable federal, state, or local laws.

The informed consent requirements in these regulations are not intended to preempt any applicable federal, state, or local laws that require additional information to be disclosed in order that informed consent be legally effective. Some states, such as California and Oregon, require further action on the investigator's part concerning patient consent.

Institutional Review Board (IRB) Ethic Review Committee (ERC) Review/Approval

The protocol and informed consent for this study, including advertisements used to recruit participants, must be reviewed and approved by an appropriate IRB/ERC prior to enrollment of participants in the study. It is the responsibility of the investigator to assure that all aspects of the ethical review are conducted in accordance with the current Declaration of Helsinki, International council for Harmonization (ICH) Good Clinical Practices, and/or local laws, whichever provide the greatest level of protection. A letter documenting the IRB/ERC approval which specifically identifies the study/protocol and a list of the committee members must be received by the sponsor prior to initiation of the study. Amendments to the protocol will be patient to the same requirements as the original protocol.

A progress report with a request for re-evaluation and re-approval will be submitted by the investigator to the IRB/ERC at intervals required by the IRB/ERC, and not less than annually. A copy of the report will be sent to the sponsor.

When the sponsor provides the investigator with a Safety Report, the investigator must promptly forward a copy to the IRB/ERC.

After completion or termination of the study, the investigator will submit a final report to the IRB/ERC and to the sponsor, if required. This report should include: deviations from the protocol, the number and types of participants evaluated, the number of participants who discontinued (with reasons), results of the study, if known, and significant AEs, including deaths

Study Files

The investigator is required to maintain complete and accurate study documentation in compliance with current Good Clinical Practice standards and all applicable federal, state, and local laws, rules, and regulations related to the conduct of a clinical study.

Patient Confidentiality

The anonymity of participating patients must be maintained. Patients will be identified by their initials and an assigned patient number on CRFs and other documents submitted to the clinical monitor. Documents that will be submitted to the clinical monitor and that identify the patient (eg, the signed informed consent document) must be maintained in strict confidence by the principal investigator, except to the extent necessary to allow auditing by the FDA, the clinical monitor, or sponsor personnel.

Investigational Product Accountability

The investigator or designee is responsible for accountability of the investigational product at the site. The investigator or designee must maintain records of the product's delivery to the site, inventory at the site, use by each patient, and return to the sponsor or alternative disposition of any unused product. These records must include dates, quantities, batch/serial/lot numbers, and expiration dates (if applicable).

The investigator should ensure that the investigational product is used only in accordance with the protocol.

1.1. Project Design

(Protocol Amendment #6). This is a Phase 1/2a, dose-escalation study of FF-10502-01. A total of up to N=161 patients with advanced solid tumors will be included in this study. In Phase 1 dose escalation, a total of up to 9 cohorts each will receive FF-10502-01 intravenously (IV) in 500 mL normal saline over a 1-hour period at doses of 8, 12, 18, 27, 40, 60, 90, 135 or 200 mg/m² weekly (Day 1, 8, 15) for three weeks, repeated every 28 days (= 1 cycle) until progression of disease. Once 6 patients are treated at the MTD in Phase 1, an additional 4 cohorts will be enrolled. Cohort 10 will enroll any patient with an advanced solid tumor who is otherwise eligible for this study (up to 20). Cohort 11 will enroll cholangiocarcinoma patients (up to 50). Cohort 12 will enroll gallbladder carcinoma patients (up to 10). Cohort 13 will enroll urothelial carcinoma patients (up to 27). Eligible patients enrolled in Phase 1 at the MTD may count towards the Phase 2a accrual.

Patients who demonstrate clinical benefit will be allowed to continue therapy with FF-1052-01 until progression of disease, observation of unacceptable adverse events (AEs), intercurrent illness or changes in the patient's condition that prevents further study participation.

During Phase 1 of the study, a Safety Review Committee (SRC) consisting of the actively recruiting investigators, the Medical Monitor, and FPHU, will review data from each cohort on an ongoing basis. Intermediate dose levels may be added if DLT is observed and it is recommended to do so by the SRC. During Phase 2a of the study, the SRC will review patient data at least quarterly and make recommendations to FPHU regarding the conduct of the trial.

The accrual for the Phase 1 dose escalation phase is expected to be 12 – 18 months. Accrual for the Phase 2a expansion phase is expected to be approximately 21 months, with the last patient followed every 3 months until death or patient's refusal to participate. The total study duration is expected to be approximately 57 months. The anticipated Phase 2a accrual rate is 3 – 5 patients per month for Cohort 10 and 1 – 2 patients with cholangiocarcinoma, gallbladder carcinoma and urothelial carcinoma (Cohorts 11, 12 and 13).

Safety will be assessed through the monitoring of AEs, clinical laboratory parameters (hematology, coagulation parameters, serum chemistry, and urinalysis), vital sign measurements, electrocardiograms (ECGs) and physical examinations.

Efficacy assessments will be determined on the basis of CT and/or MRI scans with best treatment response at any protocol-specified time point classified for solid tumors (RECIST v.1.1) and survival data (PFS and OS).

For Pharmacokinetics and Pharmacodynamics, the details of the analysis will be outlined in a separate PK/PD Report Analysis Plan.

1.2. Objectives

1.2.1. Primary Objective

To determine the safety profile, maximum tolerated dose (MTD), dose-limiting toxicities (DLT) and recommended Phase 2 dose (RP2D) in patients who receive FF-10502-01 for treatment of advanced solid tumors.

1.2.2. Secondary Objective

- To determine overall response rates
- To determine the duration of response and duration of stable disease (SD)
- To evaluate progression-free survival (PFS)
- To evaluate overall survival (OS)
- To evaluate the pharmacokinetics of FF-10502-01
- To evaluate FF-10502-01 incorporation into whole blood cellular DNA as a pharmacodynamic marker

1.3. Treatment(s)

1.3.1. Treatment Assignments

Phase 1: Following Screening, a total of up to 9 cohorts each will receive FF-10502-01 intravenously (IV) in 500 mL normal saline over a 1 hour period at doses of 8, 12, 18, 27, 40, 60, 90, 135 or 200 mg/m² weekly (Day 1, 8, 15) for three weeks, repeated every 28 days (= 1 cycle) until progression of disease.

DLT will be defined as the following drug-related events: Grade 4 thrombocytopenia of any duration; other Grade 4 hematologic toxicity lasting ≥ 7 days; \geq Grade 3 non-hematologic toxicity (excluding Grade 3 nausea, vomiting or diarrhea that is adequately controlled with supportive care and resolves to \leq Grade 2 within 48 hours); failure of Grade 3 platelets, absolute neutrophil count (ANC), or hemoglobin (Hb) to recover to Grade ≤ 1 within 4 weeks despite use of platelet and red blood cell (RBC) transfusions and/or growth factors; febrile neutropenia (defined as ANC $< 1000/\text{mm}^3$ with a single temperature of $> 38.3^\circ\text{C}$ or sustained temperature of $\geq 38^\circ\text{C}$ for over one hour); Grade 3 or 4 thrombocytopenia of any duration associated with bleeding; or other toxicity-related treatment interruption that does not resolve to \leq Grade 1 by Day 28 when the toxicity has received appropriate medical treatment.

Phase 2a: Once 6 patients are treated at the MTD in Phase 1, an additional 4 cohorts will be enrolled. Cohort 10 will enroll any patient with an advanced solid tumor who is otherwise eligible for this study (up to 20 patients). Cohort 11 will enroll patients with cholangiocarcinoma (up to 50 patients). Cohort 12 will enroll patients with carcinoma of the gallbladder (up to 10 patients). Cohort 13 will enroll patients with urothelial carcinoma (up to 27 patients). Patients enrolled in Phase 1 at the MTD will count towards the Phase 2a accrual.

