Once 6 patients are treated at the MTD in Phase 1, an additional 4 cohorts will be enrolled. Cohort 10 will enroll any patient with an advanced solid tumor who is otherwise eligible for this study (up to 20 patients). Cohort 11 will enroll patients with cholangiocarcinoma (up to 50 patients). Cohort 12 will enroll patients with carcinoma of the gallbladder (up to 10 patients). Cohort 13 will enroll patients with urothelial carcinoma (up to 27 patients).

Eligible patients enrolled in Phase 1 at the MTD may count towards the Phase 2a accrual.

Cohorts 1 to 12 (Both Phases):

Patients in Cohorts 1 to 12 will receive FF-10502-01 on a weekly schedule for 3 weeks (Days 1, 8, and 15), repeated every 28 days. The Phase 2a dose regimen is FF-10502-01 90 mg/m², administered on Days 1, 8, and 15 of a 28-day cycle.

Blood samples for PK assessment of FF-10502 plasma concentrations for patients in Cohorts 1 to 12 will be collected on Cycle 1 Days 1 and 15 pre-dose, immediately following cessation of infusion (within 15 minutes), between 1-2 hours post-infusion, and between 4-6 hours post-infusion. Incorporation of FF-10502 into cellular DNA of whole blood will be assessed as a pharmacodynamic endpoint pre-dose Cycle 1, Days 1, 8, and 15, and during the Day 22 visit.

Blood for hematology and serum chemistry determinations will be collected within 28 days before Cycle 1 Day 1, on Days 1, 8, 15 and 22 of Cycle 1, on Day 1 of each subsequent cycle and at the End of Treatment Visit. After Cycle 1, blood for hematology also will be collected pre-dose on Days 8 and 15 of each cycle. Urine will be collected for urinalysis within 28 days before Cycle 1 Day 1, on Day 1 of each cycle and at the End of Treatment Visit.

Cohort 13 (Phase 2a):

Patients in Cohort 13 (urothelial carcinoma) will receive FF-10502-01 on a weekly schedule for 2 weeks (Days 1 and 8), repeated every 21 days.

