6.2 Number of Patients and Centers

Phase 1: Up to 54 patients are planned for the dose-escalation phase, with 6 of these patients treated at the MTD.

Phase 2a: Four additional cohorts are planned; Cohort 10 (advanced solid tumors) will enroll up to 20 patients, Cohort 11 (cholangiocarcinoma) will enroll up to 50 patients, Cohort 12 (gallbladder carcinoma) will enroll up to 10 patients, and Cohort 13 (urothelial carcinoma) will enroll up to 27 patients for a total of up to 107 patients.

Entire study: Total N of up to 161 patients.

The study will be conducted at The University of Texas M.D. Anderson Cancer Center, [name]., Principal Investigator (PI) and Sarah Cannon Research Institute, Denver, CO, [name]., PI. Drs. [name] and [name] will serve as Co-PIs for the study. Once experience is gained at these institutions. Up to six additional sites may be added to complete study enrollment in a timely manner.

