8.2 Study Drug Administration

Patients should be scheduled to begin study therapy following completion of Screening.

FF-10502-01 is compatible with both dextrose 5% in water (D5W) and 0.9% sodium chloride (normal saline; NS) when diluted to a final concentration between 50 µg/mL and 1.5 mg/mL. After admixture, the final IV admixture may be maintained at room temperature or under refrigeration (2-8°C) for up to 24 hours. The infusion will be administered over a 1-hour period.

Phase 1: Patients will receive FF-10502-01 weekly IV at the dose level prescribed per cohort on Days 1, 8 and 15 of each 28-day cycle (= 1 cycle).

Phase 2a, Cohorts 10 to 12: Patients will receive FF-10502-01 90 mg/m² IV on Days 1, 8 and 15 of each 28-day cycle (= 1 cycle).

Phase 2a, Cohort 13: Patients will receive FF-10502-01 90 mg/m² IV on Days 1 and 8 of each 21-day cycle (= 1 cycle).

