11 STATISTICAL METHODOLOGY

11.1 Determination of Sample Size

Phase 1:

The sample size reflects requirements associated with a single patient dose escalation until \geq Grade 2 toxicity is observed, thereafter a 3+3 design. A total of 3 to 54 patients are planned (1 to 6 patients in each of 9 dose cohorts).

Phase 2a:

There are 4 cohorts in Phase 2a. The expansion cohorts will assess the efficacy of FF-10502-01 in a cohort of patients with a variety of solid tumors (Cohort 10), in a cohort of patients with cholangiocarcinoma (Cohort 11), in a cohort of patients with gallbladder carcinoma (Cohort 12), and in a cohort of patients with urothelial carcinoma (Cohort 13).

The primary measure of efficacy in these 4 expansion cohorts will be response according to the RECIST 1.1. criteria. A maximum of 20 patients will be accrued in Cohort 10, a maximum of 50 patients will be accrued in Cohort 11, a maximum of 10 patients will be accrued in Cohort 12, and a maximum of 27 patients will be accrued into Cohort 13.

Cohort 10: Cohort 10 will recruit patients with a variety of solid tumors to explore whether responses are seen in additional tumor types. If the overall response rate amongst these patients is 14%, there will be a less than 5% chance of failing to see a response in at least 1 patient.

Cohort 11 (cholangiocarcinoma): Historically, very low response rates have been observed in cholangiocarcinoma. Cohort 11, with a maximum of 50 patients, has 80% power if the true response rate, p_1 , is 16%, using a 1-sided type I error of 5% with a null hypothesis, p_0 , of 5%. A Simon 2-stage design will be employed so that 50 patients are only recruited if evidence of activity is confirmed at an interim analysis. If after 25 patients have been recruited, there are 1 or fewer responses, enrollment for this cohort may be suspended for futility. If after 50 patients have been recruited, 6 or more responses are observed, the null hypothesis of a 5% response rate will be rejected. An alternative analysis may include all treated cholangiocarcinoma patients—not just those meeting the definition of Cohort 11.

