Stable disease for ≥ 4 cycles (approximately 4 months) may also be of clinical benefit in this population. If the proportion of patients in this cohort having stable disease is $\geq 30\%$ after 25 patients have been enrolled and treated, enrollment into this cohort may continue until 50 patients are treated. Note that recruitment will continue past 25 patients—it will not stop until a decision is made at the interim analysis.

Cohort 12 (gallbladder carcinoma) is exploratory with 10 patients to be recruited. If the response rate amongst these patients is 26%, there will be a less than 5% chance of failing to see a response in at least 1 patient.

Cohort 13 (urothelial carcinoma) will also employ a Simon 2-stage design with 80% power, a 1-sided type I error of 5%, $p_1 = 20\%$ and $p_0 = 5\%$. If after 15 patients have been recruited, there are no responses, enrollment for this cohort may be suspended for futility. If after 27 patients have been recruited, 4 or more responses are observed, the null hypothesis of a 5% response rate will be rejected.

In both Cohorts 11 and 13, there will be no pause in recruitment prior to the interim analysis given the previous responses already observed in these indications. Furthermore, prior to any

decision to stop recruitment into a given cohort, the number of patients with prolonged stable disease will also be considered.

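### The 5% type I error of the Cohort 11 and Cohort 13 two-stage tests is not guaranteed, because Phase 1 MTD patients with already known outcomes may be counted in them

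*SAP*

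**What the plan says.** **Carry-over.** SAP 1.3.1 is unconditional: "Patients enrolled in Phase 1 at the MTD will count towards the Phase 2a accrual". Protocol 6.1 is conditional and discretionary: "Eligible patients enrolled in Phase 1 at the MTD may count towards the Phase 2a accrual". The protocol synopsis and SAP 1.1 follow the protocol 6.1 wording, so the SAP differs from the protocol and from itself. Protocol 6.2 plans up to 54 Phase 1 patients, "with 6 of these patients treated at the MTD".

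**Tests.** Protocol 11.1 gives both cohorts a Simon two-stage design with null rate 5%, 1-sided type I error 5% and power 80%.
- Cohort 11: alternative 16%. Enrolment may be suspended at 1 or fewer responses in 25; the null is rejected at 6 or more in 50.
- Cohort 13: alternative 20%. Enrolment may be suspended at no responses in 15; the null is rejected at 4 or more in 27.

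**Prior knowledge.** For these two cohorts, protocol 11.1 says that "there will be no pause in recruitment prior to the interim analysis given the previous responses already observed in these indications".

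**Schedule.** Phase 1 patients are dosed "weekly IV at the dose level prescribed per cohort on Days 1, 8 and 15 of each 28-day cycle" (protocol 8.2). Cohort 13 is dosed "on a weekly schedule for 2 weeks (Days 1 and 8), repeated every 21 days" (protocol 6.1). Protocol 11.3.2.1 sets a response window of 16 weeks for Cohorts 1-12 and 12 weeks for Cohort 13.

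**Second analysis set.** For Cohort 11, protocol 11.1 adds: "An alternative analysis may include all treated cholangiocarcinoma patients".

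**The concern.** The binomial error rate of a two-stage rule assumes that the outcomes entering the count were unknown when the rule was set, or at least that inclusion did not depend on them. Here the current rules were written after responses had been seen in both indications. Protocol 6.3 also describes Phase 1 accrual in the past tense, so the results of the MTD patients were probably available. If one of those responders is counted, the same observation both motivates the hypothesis and helps to confirm it. The futility look and the final test then both become easier to pass than stated.

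The discretionary wording is the weaker of the two. It leaves the choice of whom to count until after outcomes are known. Neither wording says whether a carried patient enters the 25- or 15-patient look.

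Cohort 13 has a further problem. A urothelial patient carried from Phase 1 would have had a different schedule and a longer response window from those the cohort is meant to evaluate.

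**Working it through.** **1. Reproduce the stated design.** The inputs are the Cohort 11 and 13 rules in protocol 11.1. With first-stage size n1, futility limit r1, total n and rejection count r,

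P(reject) = sum over x > r1 of Bin(x; n1, p) × P[Bin(n − n1, p) ≥ r − x].

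| | Error at p = 5% | Power |
|---|---|---|
| Cohort 11 (n1 = 25, r1 = 1, n = 50, r = 6) | 3.48% | 80.7% at 16% |
| Cohort 13 (n1 = 15, r1 = 0, n = 27, r = 4) | 4.27% | 81.0% at 20% |

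If the futility stop is ignored, since the protocol says only that enrolment may be suspended, the error is 3.78% and 4.37%. The stated 5% and 80% are met.

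**2. Add carried patients.** Let m patients be carried into stage 1, k of them known responders. The first-stage count becomes k + X with X ~ Bin(n1 − m, 5%); the rest is unchanged. The documents give neither m nor k. I let m run up to 6, the number planned at the MTD across all tumour types. These are probabilities of rejection at a true 5% rate, conditional on the carried results (futility stop applied):

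| Carried responders | Cohort 11 | Cohort 13 |
|---|---|---|
| k = 0, m = 1 to 6 | 3.2% down to 1.8% | 3.8% down to 1.8% |
| k = 1, m = 1 to 6 | 9.5% down to 6.5% | 13.9% down to 8.5% |
| k = 2, m = 2 to 6 | 21.8% down to 17.7% | 35.8% down to 28.3% |

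**3. Futility look.** At a true 5%, the chance of passing as designed is 1 − 0.642 = 36% (Cohort 11) and 1 − 0.463 = 54% (Cohort 13). With one carried responder and m = 1, Cohort 11 needs one more response among 24: 1 − 0.95^24 = 71%. In Cohort 13 a count of no responses in 15 is then impossible, so the look is always passed.

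**4. Inclusion that ignores outcome.** Average step 2 over the carried results at a 5% rate. For m = 1:
- Cohort 11: 0.95 × 0.0317 + 0.05 × 0.0949 = 0.035
- Cohort 13: 0.95 × 0.0377 + 0.05 × 0.1386 = 0.043

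This equals the design value, and the same holds for every m.

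**5. Inclusion that depends on outcome.** Suppose only responders were counted under the discretionary wording. With two urothelial MTD patients available, the number of responders is 0, 1 or 2 with probability 0.9025, 0.095 or 0.0025. Cohort 13 error is 0.9025 × 0.0427 + 0.095 × 0.1386 + 0.0025 × 0.3576 = 5.3%. The same sum with six available gives 7.6%. For Cohort 11 the results are 4.1% and 5.5%.

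**6. Schedule alone, Cohort 13.** Let carried patients respond at rate q on the Phase 1 schedule while the true Cohort 13 rate is 5%. At q = 5% the error is unchanged. At q = 10% it is 4.8%, 5.3% and 7.8% for m = 1, 2 and 6; at q = 20% it is 5.8%, 7.6% and 17.9%.

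**The case against.** A reader might infer that the 5% error has already failed. The documents do not support that. No passage shows that any Phase 1 MTD patient had cholangiocarcinoma or urothelial carcinoma, or responded. The earlier responses mentioned in protocol 11.1 carry no number, dose level or phase. They may have occurred at other doses, or already within Phase 2a, in which case the carry-over rule would not bring them in. Carried patients could also fall into Cohort 10, which takes any advanced solid tumour and has no test. With no carried responder the error is below 5%. The figures for one or two responders are conditional on a favourable carried result and are not unconditional type I errors. All of this stands.

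The unconditional SAP 1.3.1 wording, taken literally, leaves no room to select by outcome. That also stands, but three other statements of the rule are discretionary, and nothing says which governs.

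A reader might also infer that the schedule difference by itself inflates the error. It does so only if the response rate on the Phase 1 schedule exceeds 5%, and it does not arise in Cohort 11, whose schedule is that of Phase 1. The word *eligible*, together with the regimen given for Cohort 13, could be read as already excluding such patients, but no sentence says so.

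The alternative cholangiocarcinoma analysis is disclosed as an alternative and set apart from Cohort 11. It is a second denominator to label as supportive, not evidence of a selective one.

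Finally, response is a secondary objective, and SAP 2.4.2 and 2.4.6 plan no formal test or interim analysis. That lowers the stakes. It does not remove the point: the protocol still states when the null will be rejected, and the response rates with 90% intervals would include the same carried patients.

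**Conclusion.** The concern holds in this form: the stated 1-sided 5% error for Cohorts 11 and 13 is not guaranteed. The plan lets patients whose outcomes were already known into the counts without one agreed, outcome-independent rule.

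The size depends on unknowns. Under the assumption of 1 to 6 carried patients placed in stage 1, the conditional chance of a false rejection runs from about 1.8% with no responder to 21.8% (Cohort 11) and 35.8% (Cohort 13) with two. A single carried responder puts it above 5% in either cohort for every m from 1 to 6. If inclusion ignores outcome and carried patients share the 5% rate, the error stays at 3.5% and 4.3%.

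The schedule and window mismatch concerns Cohort 13 only. It mainly changes what that cohort estimates.

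**What to change.** - Apply the 25/50 and 15/27 counts only to patients enrolled prospectively in Cohorts 11 and 13 and treated on that cohort's own schedule. The design then has error 3.5% and 4.3% and power 80.7% and 81.0%.
- Report Phase 1 MTD patients and other off-cohort cholangiocarcinoma or urothelial patients in a separate supportive row, without a test. The alternative cholangiocarcinoma analysis belongs there too.
- Use one carry-over sentence in the protocol synopsis, protocol 6.1, SAP 1.1 and SAP 1.3.1. State that carried patients do not enter the two-stage counts.

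**Cost.** The change to the documents is wording, and the cohort caps stay as they are. Up to 6 slots in total, across all tumour types, are no longer saved and would be filled by new patients. At the 1 to 2 patients per month in protocol 6.3, the extreme case of all six falling in these cohorts is 6/2 = 3 to 6/1 = 6 months of accrual. Fewer carried patients with these tumours would cost proportionately less.
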